6.5.4.3 Urinalysis

A urine specimen will be obtained at Visit 8A (Group 2 and Group 1 if more than 28 days has lapsed since Visit 8 of the Core study), Visits 9, 10, 12, 13 and 15 for routine urinalysis, including microscopic examination.

6.5.5 Pregnancy and assessments of fertility

Serum pregnancy tests (β -hCG) will be performed at Visit 8 of the Core study or Screening visit (for Group 2) and at the final visit (Visit 15) of the Extension study. Urine pregnancy tests will be performed at Visit 9 and Visit 12, prior to study drug infusion. The test will be conducted for all female patients of childbearing potential.

[For sites where additional safeguards are required only due to local regulations e.g. UK, Italy, Germany, Sweden & etc.,: an additional supervised urine pregnancy test will be conducted at Visit 11 (Month 15) 90 days after first study drug administration. In case of a positive test, the patient must contact the investigator immediately.]

6.5.6 Bone safety monitoring

Measurement of LS-BMD Z-score at Visit 12 and 15 will be subject to monitoring from the central imaging lab for the detection of excessive changes in BMD. Repeat scans may be requested if technical factors are suspected to be involved. The investigator will be notified in the case of an absolute change in LS-BMD greater than -0.5 compared with screening at the Month 6 or 12 visits or an absolute increase of LS-BMD of greater than +2.0. In either event, the investigator should further assess the patient for secondary causes (e.g. underlying disease). If it is in the best interests of the patient to discontinue the study, discontinuation procedures should be followed as described in [Section 5.6.2](#)

6.5.7 Appropriateness of safety measurements

Safety assessments consist of monitoring and recording of all adverse events and serious adverse events, including those known to be associated with bisphosphonate use; renal function (serum creatinine and GFR), regular monitoring of hematology, blood chemistry and urine values, regular measurement of vital signs and the performance of physical examinations including oral examinations for exposed bone. An oral examination of the gums and roof of the mouth will be performed as part of the physical examination at screening, randomization, Month 6 and Month 12 visits to assess for signs of ONJ. ONJ is characterized by exposed bone in the maxillofacial area that occurs in association with dental surgery, or occurs spontaneously, with no evidence of healing. See Section 3.6.

Tanner staging assesses the sexual maturity of the patient and is important to indicate child-bearing potential in girls as these girls will require pregnancy tests before each infusion.

[figure not shown]
Vitamin D (25-hydroxy-D) and calcium will be measured before the first infusion in the Extension study to ensure that all patients have adequate vitamin D and calcium levels at

study entry, as a precaution to minimize the risk of developing hypocalcemia with the first zoledronic acid administration. In addition, ionized calcium will be monitored locally, before the first infusion to ensure that the patients have normal serum calcium level. Families will be counselled on the importance of a diet rich in calcium and vitamin D, and supplements recommended based at the investigators discretion.

Bone safety is monitored by the central imaging laboratory via DXA at Visits 12 and 15. In case of excessive change in LS-BMD Z-scores compared with the relevant baseline for each Group, the investigator will be alerted.

Patients may be hospitalized at the discretion of the primary investigator for observation following the first study drug infusion. Alternatively, they may be treated in an out-patient setting. Ionized calcium will be monitored pre-dose during this visit.

The safety assessments selected are standard for this indication/patient population.

6.6.3 Pharmacokinetics

Not applicable.

6.6.4 DNA Sampling

Pharmacogenetics/pharmacogenomics

Not applicable.

6.6.5 Other biomarkers

Not applicable.

7 Safety Monitoring

7.1 Adverse Events

An adverse event (AE) is any untoward medical occurrence (e.g., any unfavorable and unintended sign [including abnormal laboratory findings], symptom, or disease) in a patient or clinical investigation subject occurring after starting the study drug even if the event is not considered to be related to study drug. Therefore, an AE may or may not be temporally or causally associated with the use of a medicinal (investigational) product.

In addition, all reports of intentional misuse and abuse of the product are also considered an adverse event irrespective if a clinical event has occurred.

Group 1: all AEs following completion of the Core study (Visit 8) will be recorded in the eCRF of this extension study.

Group 2: due to the long screening period (at least 4 weeks), although SAEs are collected from signing the informed consent, the AE page of the eCRF is only completed from the first day of study drug; any events that occur prior to receiving study treatment, should be recorded in the eCRF as Medical History.

The occurrence of adverse events should be sought by non-directive questioning of the patient at each visit during the study. Adverse events also may be detected when they are volunteered by the patient during or between visits or through physical examination, laboratory test, or other assessments.

Abnormal laboratory values or test results constitute adverse events only if they fulfill at least one of the following criteria:

- they induce clinical signs or symptoms,
- they are considered clinically significant,
- they require therapy.

Clinically significant abnormal laboratory values or test results must be identified through a review of values outside of normal ranges/clinically notable ranges, significant changes from baseline or the previous visit, or values which are considered to be non-typical in patient with underlying disease. Investigators have the responsibility for managing the safety of individual patients and identifying adverse events. Alert ranges for laboratory and other test abnormalities are included in [Appendix 1](#).

Adverse events must be recorded on the Adverse Events CRF under the signs, symptoms or diagnosis associated with them, accompanied by the following information:

- the severity grade
 - mild: usually transient in nature and generally not interfering with normal activities
 - moderate: sufficiently discomforting to interfere with normal activities
 - severe: prevents normal activities.

There may be cases where a severe AE that is life-threatening may not necessarily be an SAE (e.g. certain laboratory abnormalities in the absence of meeting other seriousness criteria).

- its relationship to
 - study treatment (no/yes), or
 - other treatment (no/yes). or
 - both or indistinguishable
- its duration (start and end dates) or if the event is ongoing an outcome of not recovered/not resolved must be reported.
- whether it constitutes a serious adverse event (SAE - See [Section 7.2](#) for definition of SAE) and which seriousness criteria have been met
- action taken regarding investigational treatment.

All adverse events must be treated appropriately. Treatment may include one or more of the following:

- no action taken (e.g. further observation only)
- investigational treatment dosage temporarily adjusted/interrupted
- investigational treatment permanently discontinued due to this adverse event
- concomitant medication
- non-drug therapy given
- patient hospitalized/patient's hospitalization prolonged (see [Section 7.2](#) for definition of SAE)

- its outcome (not recovered/not resolved; recovered/resolved; recovering/resolving, recovered/resolved with sequelae; fatal; or unknown).

Once an adverse event is detected, it should be followed until its resolution or until it is judged to be permanent, and assessment should be made at each visit (or more frequently, if necessary) of any changes in severity, the suspected relationship to the study drug, the interventions required to treat it, and the outcome.

Information about common side effects already known about the investigational drug can be found in the Investigator Brochure (IB). This information will be included in the patient/parent/legal guardian informed consent and should be discussed with the patient/parent/legal guardian during the study as needed. Any new information regarding the safety profile of the medicinal product that is identified between IB updates will be communicated as appropriate, for example, via an Investigator Notification or an Aggregate Safety Finding. New information might require an update to the informed consent and has then to be discussed with the patient/parent/legal guardian.

The investigator must also instruct each patient and parent/legal guardian to report any new adverse event (beyond the protocol observation period) that the patient or parent/legal guardian, or the patient's personal physician, believes might reasonably be related to study treatment. This information must be recorded in the investigator's source documents; however, if the AE meets the criteria of an SAE, it must be reported to Novartis.

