7.2 Serious adverse event reporting

7.2.1 Definition of SAE

An SAE is defined as any adverse event [appearance of (or worsening of any pre-existing)] undesirable sign(s), symptom(s) or medical condition(s)] which meets any one of the following criteria:

- is fatal or life-threatening
- results in persistent or significant disability/incapacity
- constitutes a congenital anomaly/birth defect
- requires inpatient hospitalization or prolongation of existing hospitalization, unless hospitalization is for:
 - routine treatment or monitoring of the studied indication, not associated with any deterioration in condition
 - elective or pre-planned treatment for a pre-existing condition that is unrelated to the indication under study and has not worsened since signing the informed consent
 - treatment on an emergency outpatient basis for an event not fulfilling any of the definitions of a SAE given above and not resulting in hospital admission
 - social reasons and respite care in the absence of any deterioration in the patient's general condition
- is medically significant, e.g. defined as an event that jeopardizes the patient or may require medical or surgical intervention.

All malignant neoplasms will be assessed as serious under “medically significant” if other seriousness criteria are not met.

Life-threatening in the context of a SAE refers to a reaction in which the patient was at risk of death at the time of the reaction; it does not refer to a reaction that hypothetically might have caused death if it were more severe (see Annex IV, ICH-E2D Guideline).

Medical and scientific judgment should be exercised in deciding whether other situations should be considered serious reactions, such as important medical events that might not be immediately life threatening or result in death or hospitalization but might jeopardize the patient or might require intervention to prevent one of the other outcomes listed above. Examples of such events are intensive treatment in an emergency room or at home for allergic bronchospasm, blood dyscrasias or convulsions that do not result in hospitalization or development of dependency or abuse (see Annex IV, ICH-E2D Guideline).

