7.2.2 SAE reporting

To ensure patient safety, every SAE, regardless of suspected causality, occurring after the patient or parent/legal guardian has provided informed consent and until 30 days after the patient has stopped study participation (defined as time of last dose of study drug taken or last visit whichever is later) must be reported to Novartis within 24 hours of learning of its occurrence. Any SAEs experienced after this 30 day period after the patient has stopped study participation (defined as time of last dose of study drug taken or last visit whichever is later) should only be reported to Novartis if the investigator suspects a causal relationship to the study drug.

All follow-up information for the SAE including information on complications, progression of the initial SAE and recurrent episodes must be reported as follow-up to the original episode within 24 hours of the investigator receiving the follow-up information. An SAE occurring at a different time interval or otherwise considered completely unrelated to a previously reported one should be reported separately as a new event.

Information about all SAEs (*either initial or follow up information*) is collected and recorded on the Serious Adverse Event Report Form; all applicable sections of the form must be completed in order to provide a clinically thorough report. The investigator must assess the relationship of each SAE to *each specific component of study treatment (if study treatment consists of several components)*, complete the SAE Report Form in English, and submit the completed, signed form within 24 hours after awareness of the SAE to the local Novartis Drug Safety and Epidemiology Department specific to the site, and listed in the investigator folder provided to each site. The original copy of the SAE Report Form must be kept with the case report form documentation at the study site.

Follow-up information is submitted as instructed in the investigator folder. Each re-occurrence, complication, or progression of the original event must be reported as a follow-up to that event regardless of when it occurs. The follow-up information should describe whether the event has resolved or continues, if and how it was treated and whether the patient continued or withdrew from study participation.

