9.4 Analysis of the primary variable(s)

9.4.1 Variable

This study is designed to observe the long-term safety of zoledronic acid in pediatric patients who were treated with GCs and completed the Core study CZOL446H2337 (Group 1) and those who were not enrolled onto Core study due to symptomatic vertebral fracture but enrolled in this Extension study CZOL446H2337E1 (Group 2). Particular attention will be given to general safety and renal safety.

All safety evaluations will be performed separately using SAF-1 and SAF-2. The assessment of safety will be based mainly on the frequency of adverse events, serious adverse events and on the number of laboratory values that fall outside of pre-determined ranges. Other safety data (e.g. vital signs and special tests) will also be reported.

Adverse events and serious adverse events will be summarized by presenting the number and percentage of patients in which events occur, by primary system organ class, preferred term, and severity. If a patient reports more than one adverse event with the same preferred term, the adverse event with the greatest severity will be presented. If a patient reports more than one adverse event within the same primary system organ class, the patient will be counted only once with the greatest severity. Death, serious adverse events, adverse events causing permanent discontinuation of study drug, and adverse events causing concomitant medication taken will be presented by the core treatment group.

Laboratory data will be presented with respect to three groups of laboratory tests (hematology, serum chemistry, and urinalysis).

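### Protocol Section 7.1 says a life-threatening adverse event need not be an SAE, which conflicts with the SAE definition in Section 7.2.1 and could lead sites to classify laboratory events differently

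*Protocol*

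**What the plan says.** Protocol Section 7.1 lists what the site records for each AE. The severity scale has three grades and ends at "severe: prevents normal activities". Directly after the scale comes the sentence at issue: "There may be cases where a severe AE that is life-threatening may not necessarily be an SAE". Its example is "certain laboratory abnormalities in the absence of meeting other seriousness criteria". No laboratory test is named. Further down the same list, the site must record whether the event is an SAE and which seriousness criteria it meets, with a reference to Section 7.2 for the definition.

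Protocol Section 7.2.1 defines an SAE as an AE "which meets any one of the following criteria". The first criterion is that the event "is fatal or life-threatening". The section then fixes the meaning: "Life-threatening in the context of a SAE refers to a reaction in which the patient was at risk of death at the time", as opposed to a reaction that could have been fatal only had it been worse. A separate criterion covers medically significant events, including those that put the patient in jeopardy or may need intervention.

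Under Protocol Section 7.2.2 every SAE, whatever its suspected cause, "must be reported to Novartis within 24 hours of learning of its occurrence". On the analysis side, Protocol Section 9.4.1 says: "The assessment of safety will be based mainly on the frequency of adverse events, serious adverse events", together with out-of-range laboratory values. The SAP (Adverse events) gives SAEs their own table by system organ class and preferred term.

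**The concern.** The usual caution is that a severe event is not necessarily a serious one. The sentence in Section 7.1 goes further by adding that the event is life-threatening, which Section 7.2.1 treats as enough by itself. It also stands between the severity field and the seriousness field, where the site makes the classification, so a reader could take it as an exception to Section 7.2.1.

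Safety is the primary objective, and only SAE status triggers the 24-hour report, the sponsor's follow-on notification and SUSAR steps, and entry in the SAE table. Two sites could classify the same event differently, each citing the protocol.

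The example chosen is a laboratory abnormality. Two risks that the protocol itself recognises can present in that form: renal injury (Section 3.6) and hypocalcaemia after infusion (Section 5.1.2, and the data monitoring committee's concern cited in the Amendment 3 rationale). Section 6.5.7 allows outpatient treatment, so hospital admission will not always make such an event serious. The link to these two risks is an inference, because Section 7.1 names neither.

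**Working it through.** The point depends on no sample size, power or event-rate figure, so the check is a comparison of texts.

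1. **Rule in Section 7.2.1.** One criterion is enough ("which meets any one of the following criteria"), and life-threatening is a criterion. A life-threatening AE is therefore always an SAE.

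2. **Rule in Section 7.1.** A life-threatening AE that meets no *other* seriousness criterion may be a non-SAE. The word 'other' concedes that life-threatening is itself such a criterion, and the sentence then says that it may not suffice.

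3. **Can both hold?** Not if 'life-threatening' has the same meaning in both. They agree only if Section 7.1 uses the word more loosely, for an extreme laboratory value without actual risk of death.

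4. **Does the text give that looser meaning?** Section 7.1 does not define the term. The mild, moderate and severe scale has no life-threatening grade that could supply a second meaning. The only definition is the one in Section 7.2.1.

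5. **Which events are exposed?** Under Section 7.1, an abnormal laboratory value is an AE only if it causes signs or symptoms, is judged clinically significant, or needs therapy. Many such events that are also called life-threatening would meet the medical-significance criterion, and then even the Section 7.1 sentence does not exempt them. What remains is a laboratory AE that the site regards as life-threatening but, steered by Section 7.1, does not judge medically significant. This set is narrow and rests on site judgement.

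6. **Where would a misclassified event still be seen?**
   - After the first extension infusion: in the all-AE tables and, if relevant, in the SAP sections on renal-function AEs and on hypocalcaemia AEs and laboratory events. Neither of these depends on seriousness. The SAP's analysis sets contain only patients who completed the Core study, so these two analyses are specified for Group 1. For Group 2, the AE summaries in Protocol Section 9.4.1 remain.
   - Group 2 before the first dose: Section 7.1 sends events that are not SAEs to medical history.
   - After the observation period: Section 7.1 sends suspected related events to source documents, and only SAEs go to the sponsor.

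7. **Size.** The documents give no basis for the number of affected events. Section 9.6 plans about 100 patients in total. One reclassified event, in a child with no other SAE, moves the overall SAE proportion by 1/100 = 1 percentage point. In a core treatment group of 50 (assumption: all patients in Group 1, equal groups) it moves it by 1/50 = 2 points. These figures show the weight of one event, not how likely one is.

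**The case against.** The strongest defence is that Section 7.2.1 governs and Section 7.1 says so by its cross-reference. The sentence is doubly permissive, names no test and changes no reporting rule. Section 7.2.1 ties its definition of life-threatening to the SAE context, which may imply a looser everyday use elsewhere. On that reading Section 7.1 describes alarming laboratory values without real risk of death, which Section 7.2.1 also leaves out.

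Much of this stands, and it limits the consequence. A reader might infer that Section 7.1 removes life-threatening laboratory events, such as hypocalcaemia treated in an outpatient clinic, from 24-hour reporting and from the SAE count. The documents do not support that. Such an event puts the child in jeopardy and has needed intervention, so it meets the medical-significance criterion and is an SAE even for a site that follows Section 7.1 to the letter.

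Nor do the documents support the inference that the safety signal would be lost. Hypocalcaemia and renal AEs are analysed whether or not they are serious, central renal and calcium tests follow each infusion by 10 days, and the data monitoring committee's remit in Section 8.4 is not confined to SAEs.

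What does not stand is the claim that the sentence is harmless. The looser meaning has to be supplied by the reader. The medical-significance criterion calls for judgement, and Section 7.1 pushes that judgement toward non-serious. The dedicated analyses are made at the end of the trial (Sections 9 and 9.7), so they do not replace an expedited report.

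**Conclusion.** The sentence in Section 7.1 is wrong as written, because it conflicts with the rule in Section 7.2.1 that life-threatening status alone makes an AE serious. The fault is a wording inconsistency with a narrow practical reach. It could lead a site to class a life-threatening laboratory AE as non-serious, so that the event misses the 24-hour report and the SAE table and is handled differently across sites. This conclusion assumes only that some sites would read the sentence as an exception. The documents do not show that any event has been or will be misclassified, and no count can be derived. It is still worth correcting, because seriousness is the classification on which expedited reporting depends in a paediatric trial whose primary objective is safety.

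**What to change.** Delete the sentence from Section 7.1, or replace it with wording such as: *Severity and seriousness are separate judgements. A severe AE is not necessarily serious. Any AE that is life-threatening as defined in Section 7.2.1 is an SAE, including a laboratory abnormality.*

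Send a short notice to sites, and have severe laboratory AEs already recorded checked against Section 7.2.1.

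The cost is one sentence in the next amendment, the notice and the check. Amendment 3 reports 12 patients enrolled by 10 May 2016, so a check made near that date would cover few records. No new assessment or data collection is needed.
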